## 2. Adequacy of Protection Against Risks

### a. Recruitment and Informed Consent

- Efforts will be made to recruit women and minorities to participate in the proposed studies. Since the disorder being investigated affects women of all ethnicities, attempts will be made to have subjects represented from all known groups. Community screenings will be conducted in Chicago neighborhoods known to have high population densities for individuals of American Indian, Asian, and Hispanic origin. The University of Chicago has established relationships with Community- and Church-based organizations throughout the metropolitan region. These organizations will be targeted for recruitment efforts.
- Subjects will be recruited from the Outpatient Clinics at the University of Chicago, and by advertisement in appropriate newsletters or other media. The nature of the research project will be described in detail to the subjects and written summaries, in lay terms, of the research proposed will be provided for review. Written informed consent will be obtained by the P.I. from the subjects and/or parent/legal guardian where appropriate.

The protocols and consent forms have been approved by the Institutional Review Board at the University of Chicago

- Because women are the target population for the study of PCOS, the PI anticipates no difficulty in recruitment of women to participate in the proposed protocols.
- Minority populations have actively participated in the PI's research program in the past, with the distribution as noted above. As described above, outreach efforts will be intensified to ensure enrollment of underrepresented minority populations.
- Children are not specifically targeted for the present studies, nor will they be excluded. It is anticipated that a small number of children may be enrolled who are 2 years post-menarche. It is further anticipated that fewer than 5% of subjects will be less than 18 years of age.

**b. Protection Against Risk**

The following will be specifically instituted to protect human subjects from research risks:

- subjects with systemic illnesses, including heart, renal, liver, or malignant disease will be excluded. Pregnant women, women with known peanut allergy or allergy to any planned study medication will be excluded.
- The nature of the research project will be described in detail to the subjects and written summaries, in lay terms, of the research proposed will be provided for review. Written informed consent will be obtained by the P.I. from the subjects and/or parent/legal guardian where appropriate. The protocols and consent forms have been approved by the Institutional Review Board at the University of Chicago.
- The amount of blood withdrawn will be minimized to prevent significant blood loss.
- Baseline hematocrit will be measured in all subjects to ensure that this risk is not excessive. A cooling or heating apparatus will be available in the event that local venipuncture site swelling develops.
- Women will be instructed to use an effective non-hormonal form of contraception, such as condom with spermicidal foam or IUD for studies that will alter sex-steroid levels.

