**Specific Aim 2. To determine if OSA improves in women with PCOS treated with estrogen or progesterone.** For these studies, we will enroll women with PCOS who have OSA. Subjects will have a detailed baseline metabolic and metabolomic profile together with a baseline polysomnogram. Subjects will then receive a single dose of depot-leuprolide in order to suppress ovarian production of estrogen, progestin, and androgen over a period of 3 months. Six weeks after administration of depot-leuprolide, subjects will have repeated assessment of metabolic, metabolomic, and sleep measures to determine if these outcomes are altered by the combined suppression of ovarian sex steroids. Subsequently, subjects will be randomized in a double-blind placebo controlled fashion to one of two treatment arms for a period of six weeks. Treatment arms are: estrogen plus placebo or progesterone plus placebo. At the end of this second six weeks, subjects will have metabolic, metabolomic, and sleep measures repeated. Primary outcome measures will be compared both within and between treatment arms.

**Specific Aim 3. To determine if metabolic disturbances present in PCOS women with OSA are ameliorated by the treatment of OSA with continuous positive airway pressure (CPAP).** The presence of OSA in women with PCOS has a significant negative effect upon metabolic measures. In particular, the presence of OSA in PCOS is associated with hyperinsulinemia, elevations in plasma glucose, and lipid abnormalities that include higher levels of triglycerides and LDL-cholesterol. OSA in PCOS is also associated with hypercortisolemia that persists throughout both day and night. Results of our preliminary studies indicate that CPAP treatment of OSA results in attenuation of cortisol levels not only during sleep, but throughout waking hours as well. This aim will serve to test the hypothesis that correction of OSA in PCOS will lead to improved metabolic function which can be attributed, at least in part, to a reduction in circulating levels of cortisol.

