### **Screening and Specific Aim 1 Procedures, cont'd.**

**Figure D2-1. Schematic of Screening Visit. Clock time is shown along horizontal axis.**

Subjects will receive instructions on the logs/scales and practice the psychomotor vigilance test (PVT) to be used in the study. Subjects will also complete screening questionnaires including the Pittsburgh Sleep Quality Index, Berlin Questionnaire, Epworth Sleepiness Scale, Center for Epidemiologic Studies-Depression (CES-D) scale, Functional Outcome of Sleep Questionnaire (FOSQ), and the Beck Scale. An overnight full polysomnography will be performed to differentiate the subjects with from those without OSA.

For all protocols in this SCOR application the presence of OSA will be defined by an apnea-hypopnea index (AHI) of greater than 15 events per hour sleep (AHI > 15); the absence of OSA will require an AHI of less than 5 events per hour sleep (AHI < 5). This criterion is consistent with current standards and ensures that subjects with periodic limb movement disorder (PLM arousal index > 1) are excluded from study.

On the day following the full polysomnography, a 2 hr OGTT, a complete history and physical examination, routine laboratory tests (CBC, electrolytes, renal, liver function tests) and an EKG will be performed. This screening visit will also serve to familiarize the subject with the study environment and the experimental procedures.

[figure not shown]
Once the Screening Visit has been completed if the subject is deemed eligible to continue, they will be instructed on completing one week of continuous wrist actigraphy at home; subjects will be asked to maintain a standardized schedule of bedtimes and mealtimes designed in accordance with their usual habits. They will be asked not to deviate from this schedule by more than 30 minutes. During this pre-study period, subjects will also be asked to fill out a daily log of sleep and meal times. Subjects who have shown poor compliance will be given the option to repeat the week of ambulatory recordings. If compliance remains poor, subjects will be excluded from further study.

After the screening visit and completion of the ambulatory recordings, the subsequent experimental procedures depicted in Figure D2-2 and described below will occur.

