**At 15:50, a GnRH agonist test will be performed, as depicted in FIGURE D2-3 below.**

At 15:50, a 15cc blood sample for LH, FSH, estradiol, estrone, total and free testosterone, progesterone, 17-hydroxyprogesterone, and androstenedione will be obtained. At 15:59, a 5 cc blood sample will be taken for LH and FSH. At 16:00, leuprolide acetate 10 µg/kg will be given as a single subcutaneous injection. At 16:30, 17:00 and 20:00, 5 cc samples will be obtained for LH and FSH. A 15 cc sample will be obtained for estradiol, estrone, total and free testosterone, progesterone, 17-hydroxyprogesterone, and androstenedione after 16, 20, 24 hours GnRHa administration, i.e. at 8:00, 12:00 and 16:00.

As depicted in Figure D1-1, it is at this point that subjects will have completed the Screening and Specific Aim 1 Procedures. Details of procedures for subjects randomized into Specific Aim 2 or Specific Aim 3 are provided below.

### D3. Detail of methods pertaining to Specific Aims 2 and 3

The PCOS women with OSA studied in Aim 1 plus additionally enrolled PCOS women with OSA (for a total of 60 subjects) will be randomized in a ratio of 2:1 to participate in Aim 2 (n=40) or Aim 3 (n=20). Block randomization will be performed using computer-generated random numbers. The primary outcomes measure for Aim 2 is the AHI difference pre- and post-interventions, as detail in Section D3; the primary outcomes measure for Aim 3 is the change in 24 hr cortisol concentration pre- vs post-CPAP

Subjects randomized to Specific Aim 2 will have suppression of endogenous LH secretion, and thus ovarian sex-steroid production, by administration of a single intramuscular dose (11.25 mg) of the GnRH agonist depot leuprolide. Leuprolide is a synthetic nonapeptide analog of naturally occurring gonadotropin-releasing hormone (GnRH). The analog possesses greater potency than the natural hormone. When the depot form of leuprolide is administered at a dose of 11.25 mg, there is prolonged (3 month) suppression of pituitary gonadotropin levels and ovarian steroid levels as documented in the literature (115) and exemplified in Preliminary Studies. Six-weeks after administration, subjects will return to the GCRC for repeated evaluation, identical to that conducted at Baseline under Specific Aim 1.

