After this midpoint assessment, subjects will again enter into a randomized phase of the protocol. Subjects will be assigned to receive one of two treatment regimens in a randomized, double-blind, placebo controlled fashion, for a period of 6 weeks. Subjects will receive daily oral doses of either **2 mg micronized estradiol (Estrace®) plus placebo –OR– 200 mg micronized progesterone (Prometrium®) plus placebo.**

Rationale for preparation and dose of estrogen and progesterone. Natural estradiol is poorly absorbed in its native form and undergoes rapid metabolism in a first-pass effect through the liver. Thus, micronization (micronized estradiol) or acetylation (ethinyl estradiol) is required to achieve adequate blood hormone levels. Micronized estradiol is extremely well-absorbed and much of the compound is metabolized to estrone sulfate (65%) and estrone (15%). This “pool” of estrone and estrone sulfate then serves as the source of regenerated estradiol. At a dose of 2 mg per day, the steady-state levels of estradiol and estrone are typically 220 pmol/L and 68 pmol/L, respectively (116) and most closely recapitulate those seen in normal women in the midfollicular phase of the menstrual cycle (110). Because ethinyl estradiol is poorly converted to estrone, it will not be selected for use in these protocols. Micronized progesterone at a dose of 200 mg per day has been reported to result in attainment of serum progesterone concentrations typically seen in the late follicular/early luteal phase of the cycle (data provided by manufacturer).

Subjects randomized to Specific Aim 3 will be treated with nasal CPAP for a period of 6 weeks. Compliance will be documented based upon results provided by a microchip sensor that detects not only if the unit is powered on, but also if the mask is being worn by the subject. These data cannot be altered by the individual and there is no access to this microsensor by the user. The subjects who have OSA will undergo one night of CPAP titration study at the end of the baseline assessment. After 6 wks of home CPAP, the experimental study outline above will be repeated with CPAP use at night. Subjects whose average nightly CPAP use is > 5 hr will be considered compliant.

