#### **2-hour oral glucose tolerance test (OGTT)**

The 2-hour OGTT will be used as a screening test for assessment of glucose tolerance status (normal, impaired glucose tolerance and diabetes) as well as an outcome measure. After an overnight 12-hour fast, an intravenous catheter will be placed into an antecubital vein for blood drawing. Baseline samples of glucose, insulin and C-peptide will be taken at -15 and 0 minutes. At time 0, 75 g of glucose is administered orally, and blood samples are collected for the measurement of glucose, insulin, and C-peptide concentrations at 30, 60, 90 and 120 min. Diagnostic measures include baseline and 2-hour glucose concentrations. Normal glucose tolerance, impaired glucose tolerance and type 2 diabetes will be defined based upon the plasma glucose concentration at 2 h using the criteria of the Expert Committee on the Diagnosis and Classification of Diabetes Mellitus of the American Diabetes Association. Specifically, a diagnosis of normal glucose tolerance, impaired glucose tolerance, or diabetes is assigned if the glucose level at 2 h is less than 140 mg/dl, between 140 – 200 mg/dl, or 200 mg/dl or more, respectively.

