**Blood sampling and hormonal assays**

24-hour blood sampling will be performed at 15-minute intervals for 2.5 hours after each standardized meal (served at 9:00, 14:00 and 19:00) and for 2 hours after scheduled bedtime, and at 30-minute intervals at all other times for measurements of glucose, C-peptide, insulin, GH, cortisol, leptin, CRP (assayed every 4 hours), estrogen, testosterone, progesterone, acylated and non-acylated ghrelin. Blood samples will be obtained every hour for catecholamines. FFA will be obtained right before each meal and 1 hour and 2 hours after. FFA will also be obtained every hour during the night. During periods of frequent blood sampling, a sterile heparin-lock catheter will be inserted in the forearm and the line will be kept patent by a slow drip (10 cc/hr) of heparinized saline (750 IU/dl). All blood samples will be collected through the lateral arm of a three-way stopcock. During waking hours blood samples will be collected at the bedside. During sleep hours the intravenous line will be extended and fed through a light-tight port in the wall, thus allowing disturbance-free blood drawing from a next-door sampling room. The total amount of blood withdrawn during each of the proposed studies will not exceed 500 ml. Blood samples will be centrifuged immediately at 4°C and plasma will be frozen and stored at -80°C until assay. For each hormonal variable, all samples obtained from the same subject will be measured in the same assay. C-peptide, Insulin, GH and cortisol, leptin, CRP (assayed every 4 hours), estrogen, testosterone and progesterone will be measured by chemiluminescence assays using the Immulite Immunochemistry System (Diagnostic Products Corporation). Results with the DPC Immulite, as assessed by our previous experience, or according to College of American Pathologists surveys reporting use of the instrument in clinical lab settings, demonstrate sensitivity, accuracy and reproducibility that meet all the requirements of the proposed research. Ghrelin levels will be measured by RIA (Linco Research, Inc., St. Louis, MO) kit for acylated and total ghrelin. Sensitivity is 10 pg/mL.

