**c. Potential Risks**

- The clinical procedures involve a minimal discomfort associated with venipuncture. There might be slight bruising at the site that will recover in a short period of time. There is also slight risk of inflammation of the vein or infection. However, our nurses who perform these procedures are highly trained and thus these risks are minimal. The amount of blood withdrawn is minimized to prevent significant blood loss. Baseline hematocrit will be measured in all subjects to ensure that this risk is not excessive.
- There are no known direct or permanent side effects from a single injection of either diagnostic leuprolide (10mcg/kg body wt) or depot leuprolide (11.25mg). In women the changes in hormones may change the timing or pattern of the menstrual cycle during which it is given, or cause transient water retention, breast tenderness, or mood changes. Occasional patients have reported headache, GI upset, back pain, mild fever, or increased libido after a single dose of leuprolide. Swelling and tenderness at the injection site may develop. The safety of leuprolide during pregnancy and risk of treatment to an unborn fetus is unknown. Women will be instructed to use an effective non-hormonal form of contraception, such as condom with spermicidal foam or IUD.

- Insulin. Insulin administered as part of the fslVTT will raise plasma insulin levels transiently, but hypoglycemia is rare given that the insulin is administered only after a glucose bolus has been given as part of the procedure.
- Micronized progesterone will not be given to individuals with known peanut allergy since the capsules are known to contain peanut oil. Likewise, this medication will not be given to women with undiagnosed vaginal bleeding or a history of deep vein thrombosis. Patients may experience headache, breast tenderness, bloating, or depression as a result of use of this medication. Patients will be informed of these risks and all efforts will be taken to minimize them.
- Micronized estrogen will not be given to individuals with known peanut allergy since the capsules are known to contain peanut oil. Likewise, this medication will not be given to women with undiagnosed vaginal bleeding or a history of deep vein thrombosis. Patients may experience nausea, headache, breast tenderness, or bloating as a result of use of this medication. Patients will be informed of these risks and all efforts will be taken to minimize them.

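### Hematocrit is stated only at baseline although blood-intensive admissions recur about every six weeks; a repeat check with a preset sampling rule is a cheap safety improvement

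*Combined protocol and SAP*

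**What the plan says.** Section E.1.c lists blood loss among the risks and says "The amount of blood withdrawn is minimized to prevent significant blood loss". Sections E.1.c and E.2.b then give the same check: "Baseline hematocrit will be measured in all subjects to ensure that this risk is not excessive". Section D2 places the CBC on the day after the screening polysomnography, where "routine laboratory tests (CBC, electrolytes, renal, liver function tests) and an EKG will be performed". Table D1 lists neither hematocrit nor CBC.

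The volume limit is in D5, Blood sampling and hormonal assays: "The total amount of blood withdrawn during each of the proposed studies will not exceed 500 ml".

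The sampling is repeated. For Aim 2 at T2, section D3 (Detail of methods) says: "Six-weeks after administration, subjects will return to the GCRC for repeated evaluation, identical to that conducted at Baseline under Specific Aim 1". For Aim 2 at T3, section A says: "At the end of this second six weeks, subjects will have metabolic, metabolomic, and sleep measures repeated". For Aim 3, section D3 says: "After 6 wks of home CPAP, the experimental study outline above will be repeated with CPAP use at night".

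No threshold, no action on a low value and no expressly cumulative limit is given.

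**The concern.** The plan's named check on blood loss is a single value taken before the first sampling admission. It can keep out a woman who starts with a low hematocrit. It cannot detect a fall caused by the admissions themselves. A woman whose hematocrit dropped after one round of 24-hour sampling could begin the next about six weeks later without anyone seeing it. What is at stake is participant safety. The gap does not touch power, the primary analyses or the estimand.

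**Working it through.** **Where a check is stated**

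| Sampling visit | Approximate time | Hematocrit or CBC stated |
|---|---|---|
| Baseline | start | yes (baseline hematocrit; CBC at screening) |
| Aim 2 T2 | 6 weeks | not named; the word identical might bring in the CBC |
| Aim 2 T3 | 12 weeks | none |
| Aim 3 after CPAP | 6 weeks | none clearly provided |

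**Stated volumes for one full admission (D2, D5)**

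- GnRH agonist test: 15 + 5 + 3 × 5 + 3 × 15 = 80 ml.
- Frequently sampled IVGTT: 3 baseline + 27 later samples of 1 ml = 30 ml.
- Metabolomics and lipid profile: 12 + 1 = 13 ml.
- Total: 80 + 30 + 13 = 123 ml; without the GnRH test, 43 ml.

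**24-hour profile (D5)**

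- 15-minute draws after three meals: 3 × 2.5 h × 4 = 30.
- 15-minute draws after bedtime: 2 h × 4 = 8.
- 30-minute draws in the remaining 24 − 7.5 − 2 = 14.5 h: 29.
- Total: 67 draws, volume per draw not stated.

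The plan's own 500 ml figure therefore cannot be reproduced, only bracketed. Assuming 1 to 5 ml per profile draw (my assumption), a full admission takes 123 + 67 = 190 ml to 123 + 335 = 458 ml. This leaves out the six OGTT draws and any separate volume for hourly catecholamines.

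**What the cap would allow under each reading**

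- Per admission: (500 − 123)/67 = 5.6 ml per draw. The ceiling is 3 × 500 = 1,500 ml over about 12 weeks in Aim 2 and 2 × 500 = 1,000 ml over about 6 weeks in Aim 3.
- Per whole aim, Aim 3 with two full admissions: (500 − 246)/134 = 1.9 ml per draw.
- Per whole aim, Aim 2 with no GnRH test at T3: (500 − 289)/201 = 1.05 ml per draw.
- Per whole aim, Aim 2 with three full admissions: (500 − 369)/201 = 0.65 ml per draw.

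The first two whole-aim cases fall inside the assumed 1 to 5 ml; the third does not. Arithmetic alone does not settle the reading.

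**Table D1.** It lists two IVGTTs, two 24-hour profiles and two GnRH tests in each Aim 2 arm, and one IVGTT and one 24-hour profile in Aim 3. It does not say whether baseline is included. It also shows two IVGTTs for Aim 1, where the text describes one. The number of full admissions cannot be read from it.

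**The case against.** The strongest reply is that blood loss is already controlled. Volume is capped and minimized, women with systemic illness are excluded, the ethics board has approved the protocol, and baseline hematocrit is checked. These controls are real, but none of them is a repeat measurement.

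Second, the check may already be repeated. T2 is described as identical to baseline, and at least one screening-day test recurs: D5 uses the OGTT both to classify "glucose tolerance status (normal, impaired glucose tolerance and diabetes) as well as an outcome measure". This stands as a possibility for T2. It does not supply a check at T3, and the wording for the visit after CPAP does not clearly supply one. Consent pages are not in the file, so nothing can be inferred from their absence.

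Third, a reader might infer that the plan permits 1,500 ml in Aim 2 and 1,000 ml in Aim 3. The documents do not support that as a finding. Section D1 uses studies for test sessions, but D3 (Statistical Considerations) uses end of study for the end of a whole aim. If the cap is cumulative, it would answer much of the worry about volume, though it would still not detect a fall. This objection stands against any firm cumulative figure.

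Fourth, no expected hematocrit fall is given anywhere, so no harm has been shown. That also stands, and none is claimed here.

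**Conclusion.** The gap is real and modest. The plan names a risk, checks it once before the repeated exposure, and sets no rule for a low value later. It is clearest at Aim 2 T3, likely after CPAP in Aim 3, and uncertain at Aim 2 T2.

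The firm size is 123 ml of stated volume per full admission plus 67 profile draws and the OGTT draws of unstated volume. Anything beyond that rests on the assumed draw volume, the scope of the cap and the number of full admissions. The 1,500 ml and 1,000 ml figures are upper bounds under the per-admission reading only. A reader might also infer a flaw in the trial's inference; there is none here. This is an inexpensive improvement to participant safety.

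**What to change.** 1. Measure hematocrit just before each later sampling admission, alongside the pregnancy test that D1 already requires before testing.
2. Have the investigator set a threshold in advance, below which non-primary blood sampling is reduced or deferred. In Aim 2, keep polysomnography on schedule: the primary outcome is AHI, and T3 already falls about 12 weeks after a leuprolide dose with three months of effect.
3. State whether the 500 ml cap is per admission or cumulative. The sponsor should not default to the per-admission wording, which could loosen the limit if a cumulative one was meant.

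Cost: 40 × 2 + 20 × 1 = 100 routine tests if no later CBC is intended, or 40 + 20 = 60 if T2 already includes one. A small extra sample is needed where pregnancy is tested in urine. Some secondary sampling data may occasionally be lost.

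Aim 3 needs the investigator's judgment, because the 24-hour cortisol profile is itself the primary endpoint. Thinning it would affect that endpoint, while delaying it would extend CPAP beyond six weeks and require another eligible cycle window. How to handle a low value there is left to the investigator, preferably written down beforehand.
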